	Moderate cognitive impairments (T-MoCA 10-14 OR TICS-m 12-16) AND Moderate dysfunction (mRS 3 or 4)	OR Any clinical diagnosis of dementia made independent of study, e.g. by memory clinic, in primary care, recording of dementia on death certification, prescription of cholinesterase inhibitor or memantine
	Severe cognitive impairments (T-MoCA <10 OR TICS-m <12) AND Severe dysfunction	

	In a care-home OR mRS 4,5	
Death	Death (mRS 6)	Death (mRS 6)

30 Harms

These are presented as serious adverse events in Tables 6a-c and 7a-c.

31 Statistical software

Statistical Analysis System (SAS) version 9.4, SAS Institute Incorporation, Cary, North Carolina.

SECTION 7. ADDITIONAL INFORMATION

Confounding covariates

The primary outcome is recruitment, and this will be tabulated; as such, there are no confounding covariates.

The possible primary outcome in any following trial will likely be a composite comprising MACE, dementia or mild cognitive impairment, non-vascular death and new MRI signs and these event rates will be assessed in the current trial. The components are likely to be correlated. Example confounding variables are given and these are categorised by whether these were 'measured', as per routine practice, or 'unmeasured'; the latter will lead to residual confounding.

Composite outcome

Measured variables: Age, highest educational attainment, main occupation, socioeconomic status, stroke severity, function at randomisation, cognitive ability at randomisation, diabetes mellitus, hypertension, smoking, carotid disease, blood pressure, prescribed medications, time from stroke to randomisation, presence of a relevant infarct and SVD lesion severity on brain imaging.

Unmeasured: Examples are social isolation, vision, hearing, cardiac function (atrial fibrillation and heart failure are documented) and post-stroke complications.

Governance

LACI-2 is funded by the British Heart Foundation (CS/15/5/31475) and approved by the East Midlands – Nottingham 2 Research Ethics Committee (Ref: 17/EM/0077). The Sponsor is the ACCORD office, University of Edinburgh and NHS Lothian. NHS Research and Development/ Innovation approval is given at each participating site. The study is adopted by the National Institute for Health Research (NIHR) Clinical Research Network in England and the Stroke Research Network in Scotland.

Minimising bias

Multiple approaches are taken to minimise bias: central data registration with real-time on-line validation; minimisation at randomisation; blinded central postal and/or telephone assessment of outcomes; blinded adjudication of neuroimaging; inclusion of patients enrolled in other studies (co-enrolment) where feasible; analysis by intention-to-enrol (i.e. all participants) and in pre-specified subgroups.

Publications, published and planned

1. Protocol - published
2. SAP and baseline data - this publication
3. Primary results paper
4. Other secondary publications as determined by the Trial Steering Committee

Data sharing

In the future, the anonymised study data will be made available for use by external investigators in appropriate analyses upon request via a publicly accessible portal (e.g. University of Edinburgh data share). Data from LACI-2 will also be shared as appropriate with individual patient data pooling projects involving stroke and dementia; a non-inclusive list includes:

- The Cerebrovascular diseases database, Edinburgh (<https://www.ed.ac.uk/clinical-sciences/edinburgh-imaging/research/themes-and-topics/analysis-and-processing/image-databanks/cerebrovascular-diseases-image-databank>)
- Dementia Platform UK data portal (<https://www.dementiasplatform.uk/>)
- Virtual International Stroke Trials Archive-Cognition (VISTA-COG)
- Virtual International Cardiovascular and Cognitive Trials Archive (VICCTA, <http://www.virtualtrialsarchives.org>)
- META-VCI Map (<https://metavcimap.org/>)
- STROKOG (<https://cheba.unsw.edu.au/consortia/strokog>)

Similarly, anonymised neuroimaging data will be published.²⁴ The mechanisms and processes for managing external access will be determined during the course of the study. Proposals will be considered by the LACI-2 Trial Steering Committee.

ABREVIATIONS

Abbreviation	Full Text
CI	Confidence Interval
cSVD	Cerebral small vessel disease
CT	Computed Tomography
DMC	Data Monitoring Committee
ECG	Electrocardiogram
EQVAS	EuroQol-Visual Analogue Scale
EQ-5D-5L	EuroQoL- 5 Dimension- 5 Level quality of life questionnaire
F/T	Full Time
ICH	Intracerebral Haemorrhage
IMP	Investigational Medicinal Product
IS	Ischaemic Stroke
ISMN	Isosorbide Mononitrate
LACI-2	Lacunar Intervention Trial-2
LACS	lacunar syndrome
LVH	left ventricular hypertrophy
MACE	Major Adverse Cardiac Events
MI	Myocardial Infarction
MOCA	Montreal Cognitive Assessment
MRI	Magnetic Resonance Imaging
mRS	Modified Rankin scale

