9.2 PROPOSED ANALYSES

We will compare cilostazol v no cilostazol, ISMN v no ISMN, cilostazol and ISMN v neither. The proportion completing to target dose and any adverse events will be assessed using odds ratios. The LACI-2 will focus on numbers recruited, retained, tolerance and safety outcomes, blinded for TSC and unblinded intention to treat (ITT) for DMC. Safety analysis will use: Kaplan-Meier and Cox proportional regression for analysis of time-to-event outcomes of death; binary logistic regression for SAEs, recurrent stroke, MI, and in those completing 12 month MRI, the amount of microbleeds, siderosis, new infarcts, WMH burden; all adjusted for minimisation variables to maximise power.⁶⁷ We will collect data for future health economics analysis (EQ-5D-5L, EQ-VAS).

A secondary ITT analysis will be performed using logistic regression adjusted for minimisation variables of cilostazol+/-ISMN versus control on efficacy and safety outcomes, with secondary tests of subgroup interactions. Ordinal logistic regression will be used for ordinal categorical outcomes (e.g. mRS) to increase power.⁶⁸

A Statistical Analysis Plan (SAP) will be published prior to database lock and will describe analysis procedures and procedures for missing, unused or spurious data, and definitions of populations analysed.

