10.3.2 Outcome Events

The following events are **outcome events** and will be recorded as such in the eCRF. All outcome events must be assessed for seriousness and causality by the PI or a delegated trial physician. Outcome measures are not recorded as AEs or further reported to the Sponsor, unless they fulfil the criteria of seriousness as defined in section 10.1 and are deemed possibly related to the IMP. The TSC will review all outcome events six monthly blinded to treatment allocation; the DMC will review all outcomes unblinded to treatment allocation annually and on special request. These events are not of themselves reasons to automatically discontinue the trial treatment, the need for which should be assessed by the PI and attending medical staff and decisions notified to the Trials Office. The participant's wishes in the event of loss of capacity are collected on the Trial Participant Consent Form which should also be consulted.

- Bleeding
- Bruising
- Chest pain, non-specific
- Diarrhoea
- Dizziness or light headedness
- Falls
- Headache
- Heart attack
- Heartburn
- Hypotension
- Loss of mental capacity
- Nausea
- Palpitations
- Recurrent stroke or TIA

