Composite outcome for phase III	MACE, dementia, non-vascular death, new MR signs	MACE, dementia, death	MACE, cognitive decline, dependency decline, all-cause death		MACE, cognitive impairment, dependency, all-cause death
1-beta (power)	80%	80%	80%	80%	80%
Event rate, control, pa	50%	10%	30%	30%	45%
Relative risk reduction	20%	20%	20%	30%	20%
Event rate, active, pa	40%	8%	24%	21%	36%
Total sample size	950	6626	1784	778	976
Total trial size, including losses	1250	7400	2000	900	1100

MACE: major adverse cardiac events; MRI: magnetic resonance imaging

12 Framework

The primary objectives are to assess the feasibility of recruitment and adherence to medication.

13 Statistical interim analyses and stopping guidance

13a Interim analyses: Data are tabulated twice annually prior to Trial Steering Committee (TSC) and Data Monitoring Committee (DMC) meetings. No unblinded comparative analyses will be performed until data collection has been completed and the database locked.

Prior to the final database lock, the database will be subject to a soft lock and the provisional data tabulated and analysed for review by the TSC and DMC. Any final queries will be raised and resolved prior to final database lock. Members of staff still involved in the collation of data and resolution of data queries will not attend the meeting and the data reviewed at the meeting will remain strictly confidential until the point of final database lock to avoid any bias.

13b Adjustments of significance level: There is no planned adjustment.

13c Stopping rules: There are no formal stopping rules, but the DMC have responsibility to make recommendations to pause or modify the study, should there be any safety or efficacy considerations.

14 Timing of final analyses

These will be performed once data collection has been completed and the database has been locked.

15 Timing of outcome assessments

Assessments will be performed at baseline, 1-2 weeks, 3-4 weeks, 6 and 12 months (**Table C**).

Table C. Assessments at baseline and follow-up by time point (adapted from protocol and ¹).

Assessment	Prior to Baseline	Visit 1 Baseline	Week 1-2	Week 3-4	Month 6	Month 12
Screening for eligibility and consent [†]	X ^s					
Confirm and document ongoing consent		X ^s				
Medical including drug history		X ^s				
Assess MR or CT diagnostic scan; send copy to Edinburgh		X ^s				
Randomisation		X ^s				

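### SAP 13a shows analysed provisional data to the TSC and DMC before the last queries are raised, and does not say whether that analysis is pooled or by arm

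*SAP*

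**What the plan says.** SAP 13a has two paragraphs. The first covers routine twice-yearly tabulation for the TSC and DMC and ends with a rule: "No unblinded comparative analyses will be performed until data collection has been completed and the database locked". SAP 14 says of the final analyses: "These will be performed once data collection has been completed and the database has been locked".

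The second paragraph was added in SAP version 1.5. The revision history (SAP 4a) records the addition, and 4b gives no reason for it. It provides that before final lock "the database will be subject to a soft lock and the provisional data tabulated and analysed for review by the TSC and DMC". On what happens next, it says: "Any final queries will be raised and resolved prior to final database lock". Two safeguards follow. One keeps staff who are still collating data or resolving queries out of the review meeting. The other concerns disclosure: "the data reviewed at the meeting will remain strictly confidential until the point of final database lock to avoid any bias".

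The protocol separates the two committees. Section 9.2 describes the trial's main summaries as "blinded for TSC and unblinded intention to treat (ITT) for DMC", and section 10.3.2 states: "The TSC will review all outcome events six monthly blinded to treatment allocation". The same section gives the DMC unblinded outcome data every year and on request. SAP 4c says that the SAP prevails where it differs from the protocol.

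**The concern.** The usual protection in an open-label trial is that data are settled before anyone who can influence them learns how the arms compare. Here the stated order is soft lock, analysis, review by two committees, queries, final lock. If the review shows results by arm, a committee member or the analysing statistician could ask for a particular record to be checked because of where it falls. A data handler who knows nothing of the results would then carry out the query in good faith.

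At stake are the safety and efficacy comparisons that feed the decision on a phase III trial. SAP section 7 says that the plan is issued before lock so that the analyses are not driven by the data. The order in 13a leaves a gap in that protection.

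**Working it through.** The plan gives no figure on this point to reproduce. The check is to set the passages side by side.

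**1. What *locked* means and what the soft-lock analysis is.** The rule in 13a does not say which lock it means. The soft-lock paragraph does not say whether the analysis is pooled, coded or by true arm. Three readings follow:

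| Soft-lock analysis | *Locked* in the rule | Consequence |
|---|---|---|
| Pooled or coded | either | No conflict with 13a or with the blinded TSC; the text should say so |
| By true arm | final lock | Conflicts with the preceding sentence of 13a; departs from the blinded TSC |
| By true arm | soft lock | Rule satisfied if collection is complete, but results are known while records can change; departs from the blinded TSC |

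**2. Which reading is likelier.** Routine meetings receive data that are tabulated; the soft-lock data are tabulated and also analysed. Excluding staff and requiring strict confidentiality are precautions that make most sense if results by arm are shown. Most of the secondary analyses in SAP 27a are comparisons between arms. This favours the by-arm reading without proving it.

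**3. What the safeguards cover.** They govern who attends and who is told. The paragraph does not say who may raise a query after the meeting, does not exclude queries prompted by the results, and does not require changes between the two locks to be logged.

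**4. Which outcomes are exposed.** Recruitment is a known count (SAP Table 2 already shows 363 of 400). Retention is tabulated overall and not compared between arms. Both are little exposed. The comparisons in SAP 27a are exposed where a record involves judgement. Under protocol 10.8 the investigator's assessment of a serious adverse event prevails for all analyses and may be updated. Under protocol 7.2 the mRS may come from local staff when the participant cannot be reached.

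For scale only, assume that the annual rates in SAP Table A apply to all 363 patients for one year:

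- non-fatal ischaemic stroke or TIA plus non-fatal ICH: (2.5% + 0.5%) × 363 = 10.9 events
- MI: 0.6% × 363 = 2.2 events
- composite at the planned 40–50%: 0.40 × 363 = 145 to 0.50 × 363 = 182 events

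These figures show how many events the comparisons rest on. They do not measure bias.

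**5. Why the bias cannot be sized.** A calculation would need the number of queries open at or after soft lock, the share prompted by results, and event counts by arm. The documents give none of these. A query also cannot move an event from one arm to the other, because allocation is fixed at randomisation; it can only add or remove an event within an arm. Any worked p value would therefore rest on an invented split.

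**The case against.** A reader might infer that 13a flatly contradicts itself. The text does not go that far. The rule bars analyses that are both unblinded and comparative, and the soft-lock paragraph uses neither word. The SAP names two of its responsible statisticians as blinded, so a pooled or coded run fits the wording. *Locked* could also mean soft lock. This objection stands: the conflict is conditional on the by-arm reading.

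A reader might also infer that the plan lets results drive data changes. That ignores two real controls. Those who resolve queries do not see the results, and those who see the results must keep them confidential. Central follow-up and imaging reads are blinded too, and serious adverse events receive a central blinded review. These points reduce the risk. They do not remove it, because a person bound by confidentiality can still ask for a record to be checked without saying why.

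The protocol conflict has limits as well. Section 10.3.2 describes six-monthly review during the trial, not a review just before lock; SAP 4c gives the SAP precedence; and unblinded review by the DMC is already provided for. What remains is that 13a treats both committees alike where the protocol separates them, so an unclear sentence could displace a clear one.

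**Conclusion.** The point holds as a weakness of sequence and wording. The order of analysis, review, queries and final lock is stated plainly. Whether it breaches the SAP's own rule and the TSC's blinding depends on the by-arm reading, which is likelier but not stated. The existing safeguards are partial.

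The effect is confined to the safety and efficacy comparisons; the feasibility endpoint is little affected. No size can be put on any bias. Nor is this a question of type I error from an interim look: 13b plans no adjustment, 13c sets no formal stopping rule, and the review is placed at the close of the trial. It is a question of whether the last data changes can be shown to be independent of the results. The documents do not support saying that data would be changed selectively, or that any particular comparison would cross p = 0.05 as a result. The change is worth making because it is cheap and the sequence it gives is easier to defend.

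**What to change.** Amend SAP 13a to state that:

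- for any by-arm analysis outside the DMC closed session, *locked* means final lock;
- soft-lock tables for the TSC are pooled or use dummy allocation, and by-arm results at that stage go only to the DMC in closed session;
- the query list is closed before true allocation is merged with the data;
- every change between soft and final lock is logged and reported.

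Re-running the main tables on the soft-locked data as a check is optional.

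This keeps the soft lock as a quality check. The cost is a paragraph of wording, one dummy-allocation run and a change log. The downside is that the TSC sees results by arm slightly later.

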3 STUDY DESIGN

LACI-2 will be an investigator-led, Phase IIb preparatory to Phase III, prospective, randomised, 2x2 partial factorial, open label, blinded outcome trial performed in multiple hospital-based centres. The schematic in Figure 2 describes the study design. This Phase will test trial procedures and feasibility, tolerability of drug, provide safety and intermediary outcome endpoints and clinical and cognitive endpoints to power a main Phase III trial which will follow seamlessly from LACI-2 with additional funding. Brain imaging with MRI is to be used in preference to CT for diagnosis of the index stroke wherever possible, but CT is allowed.

Patients who have all of the following:

- 1) suffered a minor stroke with clinical features compatible with a lacunar stroke syndrome (designated as the 'index stroke');
- 2) on contemporaneous brain imaging have either
 - a) on MR imaging, a recent, relevant (in time and location) acute lacunar infarct on diffusion MR imaging, or
 - b) if no visible acute lacunar infarct on diffusion MR imaging then there may be a recent-appearing relevant (in time and location) acute lacunar infarct on FLAIR, T2, or T1, and
 - c) there will be no competing pathology as a cause for stroke (e.g. no acute cortical infarct on diffusion MR imaging or recent-appearing cortical infarct on FLAIR, T2, T1), no intra-cerebral haemorrhage, no stroke mimic such as tumour, or subdural haematoma);
 - d) where CT brain imaging is used soon after stroke instead of MR, a recent relevant (in time and location) small subcortical infarct (e.g. that was not present on CT prior to the stroke, or that becomes visible on a follow-up scan, if available) and no evidence of alternative causes of the stroke symptoms as in 2c above.
- 3) capacity to give consent; and
- 4) meet inclusion/exclusion criteria below (4.2),

will be randomised to start one of four treatments; isosorbide mononitrate only; cilostazol only; both isosorbide mononitrate and cilostazol; or neither isosorbide mononitrate nor cilostazol.

Patients with contraindications to cilostazol can be randomised to isosorbide mononitrate versus no isosorbide mononitrate arms only; patients with contraindications to isosorbide mononitrate can be randomised to cilostazol versus no cilostazol arms only. The partial factorial design allows testing of both drugs when given alone and together.

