Participants with an indication for or contraindication to one of the trial drugs may still be randomised to the other trial drug. If a participant allocated to both trial drugs develops a contraindication to one of the trial drugs after randomisation into the trial, then they should discontinue that drug but continue to take the other trial drug. If a patient has to discontinue either or both drugs, they should continue to be followed up in the trial as planned (unless they withdraw from the trial). Patients should remain in follow up until the end of the trial follow up period, even if they discontinue trial drug, unless they withdraw from the trial.

The study will be performed open label. Placebo tablets are not available and masking by encapsulation is too complicated and expensive. However, blinding of outcomes is important to obtain unbiased information about tolerability, safety and efficacy. As such, structured symptom questionnaires, ascertainment of clinical outcomes and MRI analysis will be collected by individuals blinded to treatment allocation.

Treatment Allocation: Participants randomised to start drug will be provided with their allocated drug/s after randomisation at the baseline visit, which they will start on the next day (i.e. day 1, week 1). In the event that there is any delay between receiving the trial tablets and starting the treatment, then the patient will receive a reminder telephone call shortly before the day that the medication should be commenced. The first day of treatment defines day 1, week 1.

Participants will be supplied with trial tablets from the hospital pharmacy to cover a maximum period of six months. Detailed dated instructions on dosing will be provided in the patient pack. The participant will be telephoned between the end of weeks 1 and 2 and between the end of weeks 3 and 4, and other times during drug introduction as necessary, as well as follow-up time points, to ensure they are taking the medication correctly.

Drugs will be provided in their packs as marketed and licensed (i.e unaltered) and dispensed by the participating hospital pharmacy under research protocols.

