54	Nil	Nil	Nil	Nil

Table 4: Patients randomised to neither Isosorbide Mononitrate or Cilostazol

Neither ISMN/Cilostazol Dosing Regime				
Day	Isosorbide Mononitrate		Cilostazol	
	Morning	Evening	Morning	Evening
1-4	Nil	Nil	Nil	Nil
5-8	Nil	Nil	Nil	Nil
9-12	Nil	Nil	Nil	Nil
13, 14	Nil	Nil	Nil	Nil
At end of study				
Week	Morning	Evening	Morning	Evening
53	Nil	Nil	Nil	Nil
54	Nil	Nil	Nil	Nil

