2. Per protocol: All consented participants with a primary outcome measure who received at least one dose of randomised medication and who had no protocol violation, e.g. they fulfilled all eligibility criteria.
3. Safety: All consented participants who received at least one dose of randomised medication.

Multiple variable analyses will include all patients with complete data for the dependent and each independent variable. All available data will be used, and missing data will not be imputed.

SECTION 5. TRIAL POPULATION**21 Screening data**

No screening logs will be kept so that data collection can be prioritised.

22 Eligibility

1. Clinical lacunar stroke syndrome.
2. Brain scanning with MR including diffusion imaging wherever possible, and obtained soon after the presentation with stroke, which showed either:
 - a. A recent, relevant (in time and location) acute small subcortical (i.e. lacunar) infarct on diffusion MR imaging.
 - b. If no visible acute small subcortical infarct on diffusion MR imaging then there is no competing pathology as a cause for stroke (e.g. no acute cortical infarct, no acute intra-cerebral haemorrhage, no stroke mimic such as tumour, subdural haematoma);
 - c. If only a CT brain scan is available, then there is a small relevant (in time and location) subcortical (i.e. acute lacunar) infarct, or if no infarct then there is no competing pathology as a cause for stroke (e.g. no acute cortical infarct, no acute intra-cerebral haemorrhage, no stroke mimic such as tumour, subdural haematoma).

3. Age >30 years.
4. Independent in activities of daily living (modified Rankin Scale <=2).
5. Capacity to give consent themselves.

23 Recruitment

Recruitment will be summarised in a CONSORT flow diagram.

24 Withdrawal/follow-up

Withdrawals, and missed follow-ups and their timing will be summarised in the CONSORT flow diagram.

25 Baseline patient characteristics

25a Baseline characteristics: These will comprise demographic, education, premorbid function, cognitive ability, medical history, blood pressure, stroke investigations, clinical and brain imaging parameters (Table 1).

25b Summarisation: Data will be shown as number (%), median [interquartile range] or mean (standard deviation) as appropriate.

SECTION 6. ANALYSIS

26 Outcome definitions

26a Specifications:

Primary endpoint

Feasibility of a Phase III efficacy trial assessed as:

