- Death, including fatal haemorrhage, aiming for less than outside the upper 95% CI of 2% per year.
- The *combined rate* of recurrent stroke, MI, death, cognitive impairment and dependency, aiming for 40-50% at one year after enrolment.

Comparison of rates of events between the treatment groups: cilostazol vs no cilostazol, ISMN vs no ISMN, and cilostazol and ISMN vs neither, for:

- Systemic or intracranial bleeding, recurrent cerebral and systemic vascular events, and vascular and non-vascular causes of death.
- Death, all cause.
- New ischaemic or haemorrhagic stroke lesion or increase in SVD lesions on MRI.
- Composite of: recurrent clinically-evident stroke, MI, death, cognitive impairment (including dementia) and dependency.
- Individual event: stroke (clinically-evident or imaging-detected ischaemic or haemorrhagic stroke to be reported separately), TIA, myocardial ischaemia, cognitive impairment and dementia.
- New infarcts and haemorrhages, absolute and change in WMH, microhaemorrhages, lacunes, atrophy imaging variables from central read of baseline imaging and one year MRI
- The comparisons of combined cilostazol and ISMN versus neither, whilst being very underpowered statistically, are presented since these may be the two groups studied in the planned follow-on trial.

Central tendency, comparisons and regressions will be analysed as follows (**Table D**).

Table D. Descriptive and analytical statistics

	Binary	Nominal	Ordinal	Continuous
Central tendency and distribution	N (%)	N (%)	Median [interquartile range]	Mean (standard deviation)
Comparisons	Chi-square (2x2)	Chi-square (2x2, or rxc)	Mann-Whitney U or Kruskal-Wallis	t-test (pooled) or 1-way ANOVA
Regression	Binary logistic regression (BLR)	-	Ordinal logistic regression (OLR)	Multiple linear regression (MLR)

27b Covariate adjustment: Analyses will be adjusted for minimisation covariates:

- Age, sex, stroke severity (NIHSS), dependency resulting from the stroke, systolic blood pressure, smoking status, time after stroke, years of education.

Covariate adjustment with continuous variables (age, NIHSS, SBP, time after stroke, years of education) will use original, not dichotomised, data.

27c Assumption checking: The assumption of proportionality will be tested using the likelihood test.

27d Alternative methods: If the data fail the assumption of proportionality (tested using the likelihood test), we will use alternative methods such as multiple logistic regression.

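### SAP section 20 defines the Safety and Per-protocol sets by receipt of a dose, which in a trial without placebo excludes everyone allocated no drug; the harm arises only if those sets are used as written

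*SAP*

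**What the plan says.** SAP section 20 defines three populations. Intention-to-treat has no dose condition. The other two do: "Per protocol: All consented participants with a primary outcome measure who received at least one dose of randomised medication" (and with no protocol violation), and "Safety: All consented participants who received at least one dose of randomised medication". Nothing there covers a participant allocated no drug.

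Such participants exist by design. Protocol 5.5.1 says "Placebo tablets are not available and masking by encapsulation is too complicated and expensive". Protocol 6.2, Table 4, headed "Patients randomised to neither Isosorbide Mononitrate or Cilostazol", shows Nil in every cell. Protocol section 3 adds a second group: "Patients with contraindications to cilostazol can be randomised to isosorbide mononitrate versus no isosorbide mononitrate arms only", and likewise for the other drug. Half of those randomised for one drug only are therefore allocated nothing.

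The SAP's safety questions need these people. Section 26a frames the death criterion as trial drugs against no trial drugs. Section 27a compares "cilostazol vs no cilostazol, ISMN vs no ISMN, and cilostazol and ISMN vs neither". Tables 6a-c, 7a-c and 8 all have no-drug columns.

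No table is labelled ITT, Per protocol or Safety. Section 30 sends harms to Tables 6a-c and 7a-c without naming a population, and the sensitivity analyses in section 27e include no per-protocol analysis.

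**The concern.** Protocol 9.1 gives tolerability and safety as the trial's main purposes, and a set named Safety is where an analyst would naturally turn for harms. As defined, it contains nobody who was allocated no trial drug.

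An analysis on that set could not compare both drugs with neither. Each single-drug comparison would still run, but against controls who were all allocated the other trial drug. For a side effect shared by the two drugs, this understates the effect of each. Headache is one: the rationale in protocol 1.2 says that both cause it. Where the other drug does not affect the outcome, only precision is lost.

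**Working it through.** **The plan's own figures.** SAP Table 2 gives 363/400 = 90.75%, printed as 90.8%. SAP section 11a sets the sample size from a 2% death rate with an upper 95% limit of 4% in 400 patients. The exact upper limit for 8/400 is 3.9%, so the figure reproduces; it counts all 400. The SAP gives no size for the Safety set.

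**Inputs.** N = 363 (SAP Table 2). Allocation is 1:1 for each drug (protocol 5.5.1). The share *s* randomised for one drug only is not given; it is assumed at 0, 10 or 20%, split equally between the drugs. Someone never randomised for a drug is assumed to be left out of that drug's control column; the SAP does not say this.

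**Formulas.**

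- Factorial cell: c = (1 − s)N/4
- All participants allocated no drug: c + sN/2
- Largest possible Safety set: N − (c + sN/2), reached only if everyone allocated a drug takes a dose
- Single-drug controls, all randomised: C = 2c + sN/4
- Single-drug controls left in the Safety set: at most c, all allocated the other drug
- Ratio of interval widths (equal variances, drug arm of size C): √[(1/C + 1/c)/(2/C)]
- Share allocated the other drug, in the drug arm and in the full control group: q = c/C = (1 − s)/(2 − s)

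| | s = 0 | s = 10% | s = 20% |
|---|---|---|---|
| Factorial cell c | 90.8 | 81.7 | 72.6 |
| Allocated no drug, excluded | 90.8 | 99.8 | 108.9 |
| Safety set, at most | 272.2 | 263.2 | 254.1 |
| Both-versus-neither controls, full → Safety set | 90.8 → 0 | 81.7 → 0 | 72.6 → 0 |
| Single-drug controls, full → Safety set (at most) | 181.5 → 90.8 | 172.4 → 81.7 | 163.4 → 72.6 |
| Ratio of interval widths | √1.500 = 1.22 | √1.556 = 1.25 | √1.625 = 1.27 |
| Controls allocated the other drug, full → Safety set | 50% → 100% | 47% → 100% | 44% → 100% |

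**Direction of the bias.** Suppose the two drugs add *a* and *b* to the risk of a symptom, additively (an assumption). In all randomised participants both sides of the contrast for the first drug carry q·b, so it estimates a. In the Safety set the drug arm still carries q·b but the controls carry b, so it estimates a − (1 − q)b. With s = 0 that is a − b/2. If the two effects are equal, the apparent effect is q·a, that is 50, 47 or 44% of the true one. If b = 0 there is no bias.

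**Cost of a dose-restricted set after correction.** If an assumed 2, 5 or 10% of those allocated a drug never start, then with s = 0 it loses 272.2 × 0.02 = 5.4, 272.2 × 0.05 = 13.6 or 272.2 × 0.10 = 27.2 participants, and none from the neither arm.

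**The case against.** The strongest reply is that no document plans an analysis on either set, so these figures measure a hypothetical. Much points to analysis as randomised:

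- Protocol 9.2 covers "tolerance and safety outcomes, blinded for TSC and unblinded intention to treat (ITT) for DMC", and separately plans a secondary ITT analysis against control on efficacy and safety outcomes. The SAP does not contradict it.
- SAP Section 7, under Minimising bias, promises "analysis by intention-to-enrol (i.e. all participants) and in pre-specified subgroups".
- The titles of Tables 4, 5, 7a-c and 9 refer to randomised groups, and Tables 5 and 9 open with a row for patients randomised.
- Version 1.5 added text to section 27a explaining why both versus neither is presented, and an empty neither column would be noticed at once.

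Most of this stands. The authors plainly mean to include untreated controls, and no planned estimate is shown to change.

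It does not repair the definition. The Section 7 term is not one of the three populations in section 20, and it differs from the SAP's ITT set, which requires a primary outcome measure. A title naming randomised groups says how people are grouped, not who is included. The single-drug columns would not empty: they would shrink and keep only people allocated the other drug, which is easier to miss.

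Table 8 (symptoms on treatment) and the During and After rows of Tables 6a-c may look like places where the Safety set will be used. That is a guess: During and After classify the timing of an event, and all these tables have no-drug columns.

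**Conclusion.** The one-dose rule is unusable for this design and contradicts the SAP's own comparisons with no trial drug. That follows from the wording and rests on no assumption.

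The consequences are conditional. They apply only to a safety analysis run on the Safety set as written, and their size rests on the assumed 0 to 20% one-drug share and on 1:1 allocation. The Safety-set counts are upper limits, because never-starters would reduce them further. The understatement also requires an outcome that the other drug causes.

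A reader might infer that the trial will discard its untreated controls, that every no-drug column would be empty, or that the main result is at risk. The documents support none of these. The no-drug columns and protocol 9.2 show that controls are intended; only the both-versus-neither control group would be empty; and ITT analyses and the primary endpoint of recruitment and retention do not use these sets.

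**What to change.** In SAP section 20, apply the one-dose condition only to participants allocated a drug. State that participants allocated no drug enter the Safety set, and enter the Per-protocol set if they meet its other conditions.

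State that the drug-versus-no-drug safety comparisons (Tables 6 to 8 and death) use all randomised participants as allocated, which protocol 9.2 and SAP Section 7 already point to. Name the population on each of these tables. Any dose-restricted set should be supportive only.

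This is a change of SAP wording before database lock and needs no new data. The one statistical cost falls on the supportive set: it loses never-starters from the drug-allocated groups only, so its groups are no longer exactly those randomised.
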